The proposed study will be carried out in two phases. The initial Vanguard phase will assess the feasibility of the trial in terms of rates of patient recruitment, percent adherence to randomization, percent data completion and percent loss to follow-up. Pre-defined criteria to determine feasibility will be a rate of randomization of ≥ 16 patients per week, with 95% adherence to randomization and an overall rate of $\geq 90\%$ data collection at 3 weeks post-SWL, and an overall loss to follow-up of $\leq 10\%$. These parameters will be assessed weekly throughout the Vanguard period. This phase of the study will continue until all target parameters have been met for 3 consecutive weeks and a minimum of 200 patients have been randomized. If these parameters are met then the Vanguard phase will be interpreted to have demonstrated feasibility and patient recruitment will continue until complete data for ≥ 1350 patients has been collected. Alternatively, the Vanguard phase may be concluded when a maximum of 300 patients or a six month period from study start date has elapsed or a modification to number of sites accruing may be considered. If the Vanguard phase fails to demonstrate feasibility, and we judge that this indicates that a significant protocol modification is needed we will close the trial and analyze available data. The data would be analyzed in accordance with pre-defined methodology and would be submitted for publication. Importantly, even if the Vanguard phase does not show feasibility, it would still provide the largest cohort of high quality data available in the literature and as such would still be an important contribution to the current state of knowledge.

The study centres, Helsinki University Hospital, University of Western Ontario St Joseph's Hospital, Université de Sherbrooke, Pontifical University Catholic of Campinas, Rede D'Or Sao Luiz, and King Abdulaziz University are each academic institutions with dedicated research staff. We estimate that total of 2000 patients will need to be screened in order to acquire complete data for 1350 patients. Accounting for a 10% dropout, up to 1500 patients may need to be randomized. Eligibility criteria include patients older than 18 years presenting for SWL who do not meet one of the pre-defined exclusion criteria. Exclusion criteria are:

- Pre-SWL urine analysis positive for nitrites
- Pre-SWL urine culture reveals $>10^5$ CFU/ml of bacteria (positive urine culture)
- Taking antibiotics for UTI or other cause
- Suspected struvite stone (based on previous stone analysis, or partial staghorn)
- Presence of nephrostomy tube
- Requiring cystoscopy and ureteral stent insertion on the day of SWL
- Presence of Foley catheter or patient on regular clean intermittent catheterization (CIC)
- Presence of urinary diversion (ie: ileal conduit)
- History of urosepsis prior to SWL
- Known allergic reaction to trial antibiotic
- Previous randomization in this trial

Patients who are eligible for inclusion will then provide written informed consent. Risks and benefits will be discussed with the patient and will include being informed of a low risk of allergic reaction, colonization with antibiotic resistant organisms, and very low risk of developing of *C.Difficile* related diarrhea, or tendon injury. Conversely, the probability of successful SWL is not likely to be

influenced by our intervention. Participants will then fill out a pre-procedure study questionnaire in which baseline and demographic information will be gathered as well as a generic International Prostate Symptom Score (IPSS) questionnaire. Patients will be assigned a randomization number that will correspond to their treatment arm. Block randomization using blocks of 10 will be carried out by a central randomization organization (www.randomize.net) using a computerized algorithm. Only the research pharmacist at each site will have access to the randomization code, which will be made available for un-blinding once statistical analysis is complete. The patient and data analyst will remain blinded to treatment allocation. To ensure patient blinding, the IV solution will be concealed within a opaque paper bag or identical oral placebo and study medication will be manufactured.

Patients routinely undergo neuroleptic anesthesia during SWL at participating centers, as such it is usual care for the patient to have a saline infusion during SWL. The choice of whether or not to administer antibiotics is usually at the discretion of the attending urologist, as there is no established standard of care. For the duration of the study, participants will be mandated to receive treatment in accord with randomization. However the attending urologist will retain the ability to break protocol in accord with their clinical judgment. Any break in protocol will be recorded as such but the data will be analyzed on an intent-to-treat basis. Ciprofloxacin was chosen as the study antibiotic as it is commonly used in everyday practice, has been used in previous RCTs on antibiotic prophylaxis pre-SWL³¹ and demonstrates a good sensitivity pattern to community acquired infections. Patients will undergo SWL with a maximum of 3000 shock waves (SW) for kidney stones and up to 4500SW for ureteric stones. Additional clinical parameters such as presence of double J, Stone characteristics and renal insufficiency will be recorded at the time of SWL by the dedicated research staff.

Patients will be asked to provide two urine samples for analysis. The first will be prior to SWL within 1 month of the procedure. On the day of procedure the patient will also complete baseline documentation. After the procedure, patients will complete follow-up documentation and a second urine culture. Urine cultures will be submitted to the laboratory or hospital most convenient for the patient at 7-14 days post-SWL and results will be forwarded to the regional site. We allow the patient to submit a urine culture at their usual laboratory in an effort to minimize the burden for the patient participating in the trial and to facilitate capture of follow-up data. This approach may be essential to capture data from patients referred from an outside institution, which may represent a significant commute. An additional advantage of this approach, in contrast to mandating the use of a central laboratory, is that it may better reflect the usual pattern of patient behavior when seeking follow-up for urinary tract symptoms post-SWL. We recognize that there may be differences in culture protocol between laboratories but we feel that these are more representative of actual practice and as such support the generalizability of the study.

Data acquisition will be continuously monitored, with regular audits to assure that data from patients who have not complied with follow-up are obtained. Patients will be asked to provide a urine sample and complete and mail the follow-up form on post-operative day 7. If the follow-up questionnaire has not been received by post-operative day 10 patients will receive a reminder phone call. A second envelope will be sent containing a requisition for urine culture and follow-up questionnaire when necessary.

Our primary outcome will be a composite endpoint comprised of:

- Positive post-SWL urine culture ($\geq 10^5$ CFU/ ml), symptoms of cystitis (defined as new onset burning sensation or pain with voiding, frequency, urgency), or pyelonephritis or urosepsis (hospital admission with fever ≥ 38.5 C).

Our secondary outcomes will be:

Version 8.1 Last modified August 21, 2018

- Bacteriuria at 7-14 days post-SWL ($\geq 10^5$ cfu/ml)
- Symptoms of cystitis (new onset burning sensation or pain with voiding, frequency, urgency)
- Pyelonephritis or urosepsis (hospital admission with fever $\geq 38.5^\circ\text{C}$)
- Change in IPSS score at 2 weeks (reported as a numerical value)

We elected to measure a composite endpoint as our primary outcome for several reasons. The decision to combine several outcomes of interest, namely new post-procedure bacteriuria ($\geq 10^5$ CFU/ml), symptomatic cystitis, pyelonephritis and urosepsis, is necessary in order to limit the sample size while maintaining appropriate statistical power. This is due to the relatively rare occurrence of serious infectious complications, such as pyelonephritis and urosepsis^{10,11}. Although preventing these complications is of great clinical interest, to study their prevention post-SWL in isolation would require a prohibitively large sample size. Therefore, the use of more common, but less severe, complications such as symptomatic cystitis and bacteriuria as surrogates is appropriate. Furthermore one would expect that if there is beneficial effect of pre-SWL antibiotics then this effect would be in the same direction for each component of our composite endpoint. For example, if there is a decrease in symptomatic bacteriuria among patients in the antibiotic arm one would also expect there to be a decrease in pyelonephritis. This biological coherence is intuitive as bacteriuria is a prerequisite for pyelonephritis. However it is likely that rates of pyelonephritis alone would not be sufficiently high to compare with statistical certainty. It remains important to report component outcomes individually as secondary endpoints to confirm concordance of the effect of the study medication across component outcomes.

Data analysis

Power and sample size calculation

The power calculation for this protocol was performed using Stata v.10.1 (StataCorp, College Station, TX). Reported incidence of bacteriuria, symptomatic UTI and pyelonephritis post-SWL vary greatly¹⁰⁻¹³. Therefore, to estimate the expected incidence of our primary outcome, we used the incidence of bacteriuria reported in the AUA Best Practice Statement on antibiotic prophylaxis¹⁷. In the AUA statement, patients undergoing SWL in the placebo arm of trials assessing antibiotic prophylaxis had a 5.7% rate of bacteriuria as compared to 2.1% among those who received prophylaxis. This represented an absolute difference of 3.6% (a 60% relative risk reduction). Therefore to achieve a power of 90% to find an absolute difference of 3.6% in the occurrence of bacteriuria, with a significance level of $p < 0.05$, 661 patients will need to be recruited in each arm for a total of 1,322 patients. Accounting for 10% loss to follow-up, the total required will be 1454, or approximately 1500 patients. Assuming that 25% of patients screened will either refuse to be randomized or will meet one of the pre-defined exclusion criteria, a total of 2000 patients will need to be screened in order to randomize 1500 patients.

Statistical analysis

Once all study data has been collected, we will report the patient characteristics at enrollment, and the primary and secondary outcomes. Comparison between RCT outcomes will be performed using Fisher's exact test for binary outcomes and Student's t-test for continuous outcomes. Lost to follow-up will be accounted for according to intent to treat analysis. Patients who are lost to follow-up will be considered not to have bacteriuria, cystitis, pyelonephritis or urosepsis and a change in IPSS of zero. This will allow us to accomplish the primary objective: to determine the impact of antibiotic prophylaxis on our primary and pre-defined secondary endpoints. We will also perform a univariate and multivariate analysis using a stepwise logistic regression model to assess predictors of our primary

outcome. This will allow us to better characterize the impact of pre-SWL antibiotic use in the context of other known risk factors for UTI.

Strengths and weaknesses of study design

There are several limitations to our proposed trial. The primary criticism may be the use of a composite endpoint as a surrogate for serious infection, which is the most important outcome that we wish to prevent with our study intervention. However, there are a number of factors that provide adequate justification for the use of a composite primary endpoint in this study. Firstly, the use of a composite endpoint will improve the study's statistical power thereby reducing the sample size requirement and associated cost and time to do the trial. Secondly, there is a clear biological coherence among the component variables included in the composite outcome. This will facilitate the interpretation of study findings, as a reduction in the composite endpoint will likely imply a reduction in each of its components. However, to confirm concordance of the effect of the intervention each component of the composite outcome will be reported independently as secondary outcome. Thirdly, each component outcome is prespecified, well defined, and has the potential to be influenced by the treatment. Importantly, the composite endpoint proposed is more inclusive of relevant clinical findings than any of the available data in the literature to date. At present the best quality data used for the AUA and EAU recommendations is based on a synthesis of several relatively small, methodologically inferior trials. Existing trials report very heterogeneous outcomes. Few studies report poorly defined "symptomatic UTI", while most trials simply report the occurrence of asymptomatic bacteriuria only, at a cutoffs which range from $\geq 10^3$ to $\geq 10^5$ CFU/ml¹⁵⁻¹⁷.

Another potential criticism of our proposed RCT is the use of the IPSS as a secondary outcome, since it has not been validated for the evaluation of UTI in men and women. Unfortunately, there are no standardized questionnaires that have been validated in either gender for UTI diagnosing. If antibiotic prophylaxis reduces the incidence of symptomatic cystitis, we feel it is important to determine if it consequently reduces LUTS and improve patient quality of life. The IPSS is the most often used quality of life measure and assessment tool for lower urinary tract symptoms and would provide this data in our RCT. We recognize that the IPSS may not be the ideal tool in this setting and should be viewed as an exploratory outcome for this study.

The principal strength of our study is that it is a large blinded RCT. RCT design controls for known and unknown confounders, and allows for a clearer assessment of antibiotic prophylaxis in the setting of SWL. The proposed RCT will also be the largest and most methodologically robust trial investigating the use of antibiotic prophylaxis to date^{13,14,15}. As well, we propose to evaluate a simple antibiotic protocol which can be easily generalized and adopted at any institution. Therefore it is reasonable to expect that the results of this study, whether positive or negative, will have significant global impact on recommendations for the use of pre-SWL antibiotics.

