To test this hypothesis we propose to conduct a large ($n \geq 1350$), multicenter prospective randomized, blinded, placebo controlled trial (RCT). We recognize that our primary question may be difficult to study due to low rates of symptomatic UTI post-SWL. Therefore we propose to undertake this RCT in two phases. The Vanguard phase, which will consist of up to one fourth of the total study population, will be used to determine feasibility. Feasibility will be assessed in terms of rates of patient recruitment, percent adherence to randomization, percent data completion and percent loss to follow-up. Using pre-defined criteria, if the study is deemed to be feasible without major protocol alterations, the Vanguard phase patients will be included in the larger study. Patient recruitment will then continue until our target population size has been reached. Should the Vanguard phase be unable to demonstrate feasibility, then the available data will be analyzed, which will still provide the largest and most methodologically robust dataset available in the literature at this time.

The results of our RCT, whether positive or negative, will contribute significantly to the existing literature as it will provide the strongest Level 1 evidence available for future meta-analyses and guidelines. If the study results show a benefit to antibiotic use the expected impact on patient care will be to reduce rates of infectious complications. Furthermore, our study will allow for a more selective use of antibiotics as several important predictors of infectious complications will be elucidated through a multivariate analysis. Conversely, a null study will provide the strongest evidence against routine prophylaxis in the literature to date and potentially decrease the unnecessary use of antibiotics among patients undergoing SWL. Consequently, this would represent a cost savings to the healthcare system and may reduce the risk antibiotic resistant bacteria.

2. Background, Rationale & Present State of Knowledge

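### If the trial closes after the Vanguard phase, the plan carries the full pre-defined analysis, including a stepwise predictor model, into a dataset with perhaps 8 to 12 events and commits it to publication

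*Combined protocol and SAP*

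**What the plan says.** Section 4 (Project Design, Methodology and Analysis) sets feasibility targets for the Vanguard phase. Meeting them requires at least 200 randomized patients. The phase may instead be concluded at 300 patients or six months, or a change in the number of sites may be considered. If feasibility is not shown and the investigators judge that a significant protocol modification is needed, the trial closes. For that branch the rule is: "The data would be analyzed in accordance with pre-defined methodology and would be submitted for publication". Section 1 adds that in this case "the available data will be analyzed, which will still provide the largest and most methodologically robust dataset" available would still result.

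The only analysis methodology in the document is the Statistical analysis section: Fisher's exact test for binary outcomes, the t-test for continuous ones, and then "We will also perform a univariate and multivariate analysis using a stepwise logistic regression model to assess predictors" of the primary outcome. Nothing limits the closure branch to feasibility or descriptive reporting, labels its efficacy results exploratory, or mentions its power.

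**The concern.** The pre-defined analysis was planned for about 1350 patients, and the closure branch would apply it to a fraction of that number. Two outputs suffer.

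The stepwise model would have about one event per candidate predictor, so whatever it selects would carry extreme and unstable odds ratios. Section 1 intends these predictors to support more selective antibiotic use, so a published table of this kind could be taken at face value.

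The arm comparison would have low power at the planning rates, so a significant result would tend to overstate the benefit. The plan commits to publishing this dataset and describes it as the largest and best available, with no caution attached.

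**Working it through.** **Inputs.** Power and sample size calculation section: placebo "had a 5.7% rate of bacteriuria as compared to 2.1% among those who received prophylaxis", used as the expected rate of the composite primary outcome; alpha 0.05; power 90%. Section 4: 200 (minimum to show feasibility) and 300 (maximum). Candidate predictors: six named in section 1 (age, gender, UTI history, comorbidities, stone size, stone location) and two recorded under section 4 (double-J stent, renal insufficiency), eight in all.

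**The plan's own figure.** The two-sided two-proportion formula gives 606 per arm without continuity correction and 661 with it. This matches "661 patients will need to be recruited in each arm for a total of 1,322 patients", so the planning calculation is sound and can serve as the base.

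**Events in the closure branch.** The average rate is (5.7% + 2.1%)/2 = 3.9%.
- 200 patients: 200 × 0.039 = 7.8 events; 7.8/8 = 0.98 per candidate.
- 300 patients: 300 × 0.039 = 11.7 events; 11.7/8 = 1.46 per candidate.
- 1350 patients, for comparison: 1350 × 0.039 = 52.7 events; 52.7/8 = 6.6 per candidate.

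The plan counts patients lost to follow-up as event-free. With 10% lost, the first two counts fall to 7.0 and 10.5.

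**Stepwise model.** Forward selection at p < 0.05 was simulated with treatment plus eight predictors that have no effect. The predictor prevalences (10% to 40% for the binary ones) and the selection rule are assumptions, because the plan gives neither. Two independent simulations gave:

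| Patients | At least one null predictor selected | Median selected odds ratio | Share above 20 |
|---|---|---|---|
| 200 | 32% and 37% | about 11 and 8 | 46% and 36% |
| 300 | 38% and 38% | about 6 and 6 | 34% and 30% |
| 1350 | 28% | about 2 | not reported |

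The selection rate is close to 1 − 0.95^8 = 34% at every size. What the small sample adds is the size of the odds ratios, many of them from separation.

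**Arm comparison.** Exact enumeration of two binomials, two-sided Fisher test at p ≤ 0.05, true difference 3.6 points:
- 100 per arm: power 13.7%; mean significant difference 7.9 points (7.93/3.6 = 2.2 times).
- 150 per arm: power 24.7%; mean significant difference 6.4 points (6.38/3.6 = 1.8 times).
- At either size, significance needs at least 6 v 0, 8 v 1 or 10 v 2 events.
- With equal rates of 2.1% to 5.7% in both arms, the type I error is 0.5% to 2.3% (100 per arm) and 1.3% to 2.6% (150 per arm).

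**Sensitivity.** The first three rows are for 200 to 300 patients with the same relative effect. The Background cites bacteriuria of 8% to 23%; 14% is an intermediate value. The last two rows are assumed scenarios.

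| Scenario | Events | Power | Overstatement |
|---|---|---|---|
| Placebo rate 8% | 11–16 | 24–39% | 1.5–1.8 times |
| Placebo rate 14% | 19–29 | 48–70% | 1.2–1.4 times |
| Placebo rate 23% | 31–47 | 77–92% | 1.04–1.13 times |
| Unrelated symptoms in 10–30% of both arms, 200–300 patients | 27–98 | 5–10% | 3.1–6.6 times |
| Stop at six months with 100–150 patients | 3.9–5.9 | 2–8% | 2.7–3.7 times |

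The last row is possible because 200 is not a floor on failure: accrual below 200/26 = 7.7 patients per week ends the six months short of it.

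**The case against.** The strongest reply is that keeping a pre-specified analysis after early closure guards against post-hoc choices, and that publishing avoids selective reporting. The branch is also doubly conditional, needing both failed feasibility and a judgement that a significant modification is required. The authors know that small trials are weak: section 2 criticises earlier ones as underpowered. All of this stands. It argues for keeping publication and a fixed rule, but not for carrying over a regression that the data cannot support.

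Several stronger readings are tempting and do not hold:
- A reader might infer that any positive finding from this branch would be badly exaggerated. The two-fold figure is an average over significant results at the planning rates. Those are bacteriuria rates, whereas the composite also counts symptoms, and at a 23% placebo rate the overstatement nearly vanishes.
- A reader might infer a raised risk of a false arm difference. Fisher's test is conservative here, so that risk is below the nominal 5%.
- A reader might blame the small sample for the selection of null predictors. That rate is similar at every size.
- A reader might take the stepwise model as expressly ordered for this branch. Section 4 does not name it. It follows from the reference to pre-defined methodology, of which the document has only one.
- A reader might conclude that the Fisher test should be banned. That gains little, since an exact interval carries much the same information and is open to the same selective reading.

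**Conclusion.** The concern holds in a limited form. The closure branch has a stated analysis rule, and its natural reading includes a predictor model with about 1 to 1.5 events per candidate at the planning rates, whose output would be unreliable. The same rule gives an efficacy comparison with 14% to 25% power, in which a significant difference would on average be 1.8 to 2.2 times the true one.

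These sizes rest on 5.7% v 2.1% applying to the composite and on 200 to 300 patients. They shrink if true events are more frequent with the same relative effect. They grow if symptoms unrelated to infection count as events, which is plausible because section 2 accepts that stone debris and stents cause such symptoms, or if the phase stops early with fewer patients. The odds-ratio figures also depend on assumed predictor distributions and an assumed selection rule. The analysis of the full trial is not affected.

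**What to change.** In section 4, replace the sentence on analysis after closure with a rule specific to that branch:
- The feasibility measures are the main result.
- Event counts by arm and risk differences with exact 95% confidence intervals are reported for the composite and each component, labelled exploratory pilot data for pooling.
- The univariate and stepwise or multivariable predictor model is not run.
- The pre-specified Fisher p-value may be kept, labelled exploratory.

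The commitment to publish should stay. The cost is one or two sentences and the loss of a predictor table that could not be estimated reliably.

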Full title:

A Multicenter Randomized Controlled Trial Assessing the Efficacy of Antimicrobial Prophylaxis for Extracorporeal Shock Wave Lithotripsy on Reducing Urinary Tract Infection

Brief Title:

Antibiotic Prophylaxis Before Shock Wave Lithotripsy (APPEAL)

1. Objectives & Specific Aims

The lifetime risk of developing nephrolithiasis has been reported between 1-15%, with a prevalence of approximately 5% in North America. SWL is a very common first line treatment for ureteral and renal calculi. One of its benefits is that it has few complications. However, infection remains an important complication of the procedure. Because of this risk the American Urological Association recommends pre-SWL antibiotics for all patients. However, this approach is controversial because studies to date are of poor quality and there is concern over antibiotic resistance. Therefore the European Association of Urology recommends only selective use of antibiotics pre-SWL. To resolve this conflict and establish the most appropriate strategy for Ontarians, we propose to perform a randomized trial comparing pre-procedure antibiotics to no antibiotics among patients who undergo SWL.

The primary goal of our study is to evaluate the impact of antibiotic prophylaxis on the rate of bacteriuria, symptomatic UTI, pyelonephritis and urosepsis among patients with sterile urine undergoing SWL. Our secondary goal is to determine pre-procedural characteristics that can define patient subgroups with the greatest benefit from prophylactic antibiotics.

We hypothesize that a single dose of intravenous ciprofloxacin immediately prior to SWL will decrease the relative incidence of bacteriuria, symptomatic UTI, pyelonephritis and urosepsis by 60% or greater. Additionally, we anticipate that pre-operative patient and stone characteristics such as age, gender, history of UTI, patient comorbidities, stone size, location, may be predictive risk factors that can be used to optimize patient selection for pre-operative antibiotic use.

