Based on the existing literature, a prominent area of concern that emerges is how to define a positive urine culture and how to assess for symptomatic urinary tract infection. Previous studies have used a variety of bacterial concentration cutoffs for the definition of a positive culture¹³. We will use the most common historically accepted definition ($\geq 10^5$ CFU/ml) to define a conservative estimate of bacteriuria for the primary and secondary endpoints of our study³⁶. To define a symptomatic UTI we will capture symptoms in two different ways. We will use a predefined questionnaire in a systematic way asking patients to identify both the presence and absence of lower urinary tract symptoms as well as to quantify the magnitude of these symptoms on a scale from 0 to 5. We recognize that the passage of stone debris or presence of stent can cause lower urinary tract symptoms, but believe that appropriate randomization over a sufficiently large cohort will control for this confounder.

In addition we will evaluate the IPSS score as a quality of life measure for lower urinary tract symptoms post-SWL. We believe this is important as symptoms of UTI related to SWL may worsen IPSS scores and correlate to decreased quality of life. It is therefore of benefit to evaluate whether pre-operative antibiotic use can impact on this aspect of patient care. Unfortunately there have not been any systematically validated questionnaires that can be used to diagnose urinary tract infections among men and women. The urinary tract infection symptom assessment questionnaire (UTISA) has been validated to track resolution of UTI symptoms among symptomatic women. However it is not diagnostic nor has it been validated in men³⁷. We have chosen to use the IPSS, as it has been widely validated for the description of lower urinary tract symptoms in men³⁸⁻⁴⁰. It IPSS has also been frequently used to define lower urinary tract symptoms in women in several clinical contexts⁴¹⁻⁴⁴. We recognize that it has not been shown to be useful in the evaluation of bladder outlet obstruction in women⁴⁵, a pathology that we are not assessing in our RCT.

3. References

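### The culture cut-off is above 10^5 CFU/ml at entry but 10^5 or more at follow-up, so the endpoint can count bacteriuria already present before SWL

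*Combined protocol and SAP*

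**What the plan says.** The exclusion list in section 4 (Project Design, Methodology and Analysis) contains the criterion "Pre-SWL urine culture reveals $>10^5$ CFU/ml of bacteria (positive urine culture". The inequality is strict, and the parenthesis labels such a culture as positive. The only other exclusion based on a urine test is a nitrite-positive urinalysis.

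Further on in section 4, the culture component of the primary composite is "Positive post-SWL urine culture ($\geq 10^5$ CFU/ ml", and the matching secondary outcome is "Bacteriuria at 7-14 days post-SWL ($\geq 10^5$ cfu/ml". Both include the value 10^5 itself. Section 2 gives the same rule for the primary and secondary endpoints: "We will use the most common historically accepted definition ($\geq 10^5$ CFU/ml) to define a conservative estimate of bacteriuria".

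Section 1 states the aim for outcomes "among patients with sterile urine undergoing SWL". The paragraph in section 4 that justifies the composite describes its first component as "new post-procedure bacteriuria ($\geq 10^5$ CFU/ml". In the outcome definitions themselves, new onset qualifies the cystitis symptoms only.

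**The concern.** A culture of 10^5 is negative at entry and positive at follow-up. Read literally, the plan admits a patient at that value and scores an event if nothing has happened to the urine between the two samples. The trial asks whether a single dose before SWL prevents infection after it. Bacteriuria that was there beforehand is not the incident event it sets out to measure.

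Nothing in the planned analysis removes such cases. Under Statistical analysis, binary outcomes are compared by Fisher's exact test, with no reference to the baseline culture. Follow-up cultures go to the laboratory or hospital most convenient for the patient, so no central laboratory settles borderline counts. An eligibility criterion is applied as written at every site.

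**Working it through.** **1. The two rules side by side**

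| Baseline culture (CFU/ml) | Excluded at entry (rule: >10^5)? | Event if unchanged after SWL (rule: ≥10^5)? |
|---|---|---|
| below 10^5 | no | no |
| exactly 10^5 | **no** | **yes** |
| above 10^5 | yes | not enrolled |

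The rules disagree only in the middle row. Two other pieces of text might close the gap:

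- *Nitrite exclusion.* This is a separate test. It may remove some patients at 10^5, but it sets no culture threshold.
- *The word new.* It stands in the rationale, is not defined there, and is absent from the culture component of the outcome definitions.

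The gap remains in the operative text.

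**2. The plan's own sample size**

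Inputs from Power and sample size calculation: p1 = 0.057, p2 = 0.021, power 90%, significance level 0.05 (taken as two-sided). Then d = 0.036 and the mean rate is 0.039.

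- Uncorrected: n = [1.960·√(2·0.039·0.961) + 1.282·√(0.057·0.943 + 0.021·0.979)]² / 0.036² = (0.5366 + 0.3493)² / 0.001296 = 605.6, so 606.
- Continuity-corrected: n' = (605.65/4)·[1 + √(1 + 4/(605.65·0.036))]² = 660.03, so **661**, which is the stated figure.

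These rates make no allowance for positives carried over from baseline, so aligning the cut-offs leaves 661 as it is.

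**3. What carried-over cases could do to power**

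The documents do not give the share of patients at exactly 10^5. Let x be the points that carried-over cases add to the placebo rate. This x is an assumption, and the range below is for scale only. The sample is 1,350/2 = 675 per arm, the test is the two-sided exact Fisher test at 0.05, and the outcome is bacteriuria alone.

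- Model A, no clearance by the study drug: (5.7 + x)% against (2.1 + x)%.
- Model B, half cleared in the ciprofloxacin arm: (5.7 + x)% against (2.1 + x/2)%.

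| x (points) | x as a share of 1,350 | A: risk ratio | A: power | B: risk ratio | B: power |
|---|---|---|---|---|---|
| 0 | 0 | 0.37 | 92.0% | 0.37 | 92.0% |
| 0.25 | about 3 | 0.40 | 90.2% | 0.37 | 92.6% |
| 0.5 | about 7 | 0.42 | 88.4% | 0.38 | 93.2% |
| 1 | about 14 | 0.46 | 84.6% | 0.39 | 94.2% |
| 2 | 27 | 0.53 | 77.6% | 0.40 | 95.9% |

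Under A, x equals the share of patients at 10^5 only if every one of them is still positive at follow-up. If half persist, a 1% share gives x of about 0.5, and power is 88.4% rather than 84.6%.

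**The case against.** The best case against the point is that it is a drafting slip with little consequence. The rationale already speaks of new bacteriuria, and the exclusion criterion is glossed as a positive culture, which section 2 sets at 10^5 or more for the endpoints, so the intent is visible. Few patients may sit exactly on the boundary. If laboratories report only a top category such as above 10^5, none will; the documents give no reporting format. The baseline sample may be up to a month old at SWL, so some growth may have gone by follow-up. All of this stands, and it limits the size of the problem. It does not remove the contradiction, because sites and analysts work from the criterion and the outcome definition, and neither carries the intended rule.

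A reader might infer three stronger things that the documents do not support:

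- *That the mismatch lowers power or pulls the risk ratio towards 1.* This needs the study antibiotic to have no effect on bacteria already present. No section says so, and with half of the cases cleared, power rises slightly. The figures also concern bacteriuria alone. The primary outcome adds symptoms and admissions, and power for that composite has not been worked out here.
- *That one arm is favoured at entry.* Randomization should balance boundary patients between arms.
- *That the mismatch alone breaks the sterile-urine population.* The protocol in effect treats sterile as below a cut-off. Growth just under 10^5 would still be admitted after the correction.

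**Conclusion.** The point holds as an inconsistency in current, operative text: one culture result is classified differently at entry and at follow-up, and the primary and bacteriuria endpoints can therefore include cases that preceded SWL. That conclusion needs no numerical assumption.

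Its practical size is unknown and probably small. In the worst case considered (0.25 to 2 points added equally to both arms, no clearance), power for bacteriuria falls to between 90.2% and 77.6%. With half of the cases cleared by the study drug it does not fall. Neither the size nor the direction of the power effect can be settled from the documents. Even where power is kept, the comparison would mix clearance of existing bacteriuria with prevention of new bacteriuria. Severity: minor consistency correction.

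**What to change.** - In the exclusion criteria of section 4, change the culture threshold to ≥10^5 CFU/ml, so that it matches section 2 and the outcome definitions.
- In the primary outcome and the bacteriuria secondary outcome, state that the culture component counts only new bacteriuria: a post-SWL culture of ≥10^5 CFU/ml in a patient whose baseline culture was below that cut-off. This reconciles the definitions with the rationale. Once the exclusion is aligned, the clause matters only for patients enrolled in error, but it fixes in advance how they are classified.

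The cost is one symbol, one short clause, and a few borderline patients who become ineligible. The requirement of 661 per arm does not change.
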